Cover Page

ID: 1147099-1 Primary Care Brief Mindfulness Training for Veterans With PTSD NCT03352011

Date: October 25, 2022

Posttraumatic Stress Disorder (PTSD) is highly prevalent in Veterans Health Administration (VHA) primary care patients (~11.5%) and is associated with significant functional impairment, compromised health, and economic costs. Although effective psychotherapies for PTSD are available in specialty mental health care settings, primary care patients do not routinely follow through on referrals for a number of reasons, including fears about stigma or reluctance to disclose emotional problems. When Veterans do engage in evidenced-based PTSD psychotherapies, approximately 1/3 to 1/2 either drop-out or do not adequately respond. Therefore, alternative delivery models are needed to provide primary care patients with treatment for their PTSD symptoms and functional concerns. This application integrates two lines of research: mindfulness training and peer-support services to test a low-stigma intervention in primary care: Primary Care Based Mindfulness Training (PCBMT).

Mindfulness training is a patient-centered approach based on the belief that at the core of every individual is enormous potential for healing. We propose that the skills taught in mindfulness training (e.g., attentional control, present focus, non-judgement, acceptance, and compassion) will impact two specific outcomes for primary care veterans with PTSD: 1) reduce psychosocial distress and dysfunction (including PTSD symptoms) and 2) serve as a gateway to more intensive treatments for Veterans who are not yet willing to discuss their trauma histories or transition to a specialty care environment. Our previous research demonstrated that participation in PCBMT (a 4-session version of Mindfulness Based Stress Reduction [MBSR]) was associated with significant reductions in PTSD severity compared to primary care treatment as usual. However, PCBMT was delivered by a non-VHA expert facilitator and only 55% of Veterans attended the first mindfulness class. Therefore, further protocol refinement is needed before full-scale testing can occur.

We propose that the addition of peer support services to PCBMT will both increase veteran participation in mindfulness training and maximize veteran benefits for the two primary PCBMT outcomes: reduction of psychosocial distress and engagement in additional mental health treatments post-PCBMT. Empirical evidence demonstrates that peer support is associated with improved social functioning and engagement in treatment. Within PCBMT, peers can 1) provide a low-stigma introduction to mindfulness training prior to the first formal class, 2) help "interpret" class material to make it more personally meaningful to Veterans, 3) make ecologically valid suggestions on how participants can apply mindfulness skills to address daily struggles with PTSD-related concerns, 4) decrease social isolation by role modeling healthy social interactions during mindfulness classes, 5) provide hope for recovery by sharing their own recovery story, and 6) connect patients to additional services by acting as peer navigators.

This application aims to refine our existing PCBMT to be co-delivered by VHA mental health providers and peer support specialists and then test important aspects of feasibility to prepare for a future full-scale pragmatic clinical trial. We propose to first gather feedback from mental health providers and peers to further refine PCBMT. For this phase, providers and peers will participate in a PCBMT led by study investigators who are certified MBSR instructors. Next, study staff will gather feedback from the trained providers and peers for further adaptation and implementation. After this, providers and peers interested in being trained as PCBMT interventionists will be trained by study investigators. In the subsequent phase of the project we will conduct a pilot randomized clinical trial (RCT) comparing the refined PCBMT to a primary care-based PTSD psychoeducation group. In this pilot RCT, both treatment conditions will consist of four, 90-minute group sessions co-facilitated by a mental health provider and peer.

[figure not shown]
The long-term goal of this research is to improve clinical and personal recovery outcomes for Veterans with PTSD. Our immediate goals are to refine PCBMT based on provider, and peer feedback and then test the methods needed to conduct a future full-scale RCT, in accordance with the following aims:

1. Gather VHA mental health provider (n=5) and peer (n=5) feedback to refine PCBMT to a) ensure successful implementation in the VHA setting (including creation of a provider manual and standardized provider/ peer training curriculum), and b) maximize Veteran skill development to reduce psychosocial distress and prepare Veterans for future participation of evidence-based treatment for PTSD.
2. Assess the feasibility of conducting a pilot RCT (N=60) comparing PCBMT to a PTSD psychoeducation group on the following outcomes:
  - a. Rates of recruitment and study retention
  - b. Participant adherence and retention in treatments, provider and peer treatment fidelity
  - c. Participant acceptability (satisfaction, perceived helpfulness) in PCBMT and control condition
  - d. Measuring key outcomes to prepare for the future larger trial including: Patient well-being measured by PTSD severity, depression, health promoting behaviors, recovery orientation.

## **Study Design**

This study will provide the necessary data to apply for a NCCIH R01 focused on a full-scale trial of PC-based Mindfulness Training for Veterans with PTSD. The feasibility study will be conducted in two phases (Figure 2). Phase 1 will collect qualitative feedback on how best to refine and implement PCBMT from VHA providers and peers. Phase 2 will be a feasibility RCT comparing PCBMT to a PTSD psychoeducation group (EDU). Participants will be recruited from two neighboring sites: primary care clinics at the Syracuse and Canandaigua Veterans Affairs Medical Center.

**C.1.1 Phase 1 Participants:** VHA providers and peers will first participate in PCBMT led by certified MBSR instructors (co-Is [name] and [name]). VHA providers experienced in the treatment of PTSD will be encouraged to participate. We are selecting these providers because 1) they will know what skills (e.g. emotional regulation) will be most useful for future participation in evidence-based treatment (EBT) for PTSD and can emphasize those skills when they deliver PCBMT in Phase 2, 2) they have specialized knowledge about Veterans with PTSD, so will provide the research team with quality feedback to refine PCBMT, 3) they will be able to provide EBT for participants who opt to step-up to specialty care following PCBMT, easing the difficult transition from primary to specialty care. This protocol will involve VHA specialty MH providers delivering care in PC, which we believe will increase feasibility because PC-MHI providers often do not have time to deliver treatment outside the brief (i.e., 30 minute), population-based model. Peers will be VHA certified peer support specialists (PSS) currently employed at the Syracuse and Canandaigua VHA. Based on our recent discussion with providers and peers at our recruitment sites, we estimate that 6 providers and 4 peers will be interested and have time to participate in Phase 1. We are not eliciting feedback from Veteran patients on how to adapt PCBMT because we already obtained helpful patient feedback in our pilot study.

that are specific to PTSD such as struggles with irritability instead of examples of general stressors. 3) The loving-kindness meditation may not be well-received by all patients. After introducing it, ask participants to try it once then suggest that a previously learned, alternative sitting practices (e.g. body scan) can be used by those who don't like it. 4) I found walking meditation to be very helpful. Introduce this before the 4th session. We expect that modifications will adjust specific aspects to make the training more patient-centered and recovery-oriented, while maintaining the core mindfulness pieces.

**C.2.1 Phase 2 Participants:** For the RCT, 60 eligible patients will be enrolled and randomized to PCBMT or EDU. This sample size was chosen because it will require us to recruit 5 participants per month, which is the

Figure 2. Overview of Study Procedures

To illustrate what type of modifications may result from this feedback, possible input could include: 1) Spend less time in discussion and more time in sitting meditation. 2) When discussing how to apply a skill (e.g., non-reactivity to stress) to real life, use examples

rate of recruitment we believe we will need in a subsequent fully-powered RCT (based on a medium intervention effect size and having 3 years to recruit). We have achieved this rate of recruitment in previous studies with similar samples and methods (see B.1., B.4., B.5.).

Primary care patients will be recruited and assessed pre and post intervention and at 16 and 24 week follow-up time points. Each quarter, two months will be spent recruiting and 1 month will be used to conduct the intervention groups. Ideal group size is 6 participants. We anticipate running up three consecutive groups (PCBMT and EDU) at each of the two sites. However, our timeline allows for addition groups as needed. To be eligible, participants must be 1) enrolled in primary care at the Syracuse or Canandaigua VAMC and 2) report significant PTSD symptoms (qualifying criterion A traumatic event plus at least a 31 on the PCL-5). Exclusion criteria are minimized because we seek to include any primary care patients with troubling PTSD symptoms that would normally receive treatment in primary care. Patients will be excluded if they demonstrate symptoms that would not allow them to actively participate in PCBMT: 1) gross cognitive impairment ( $>16$  on the Blessed OMC), 2) suicide attempt or desire to commit suicide in the last month (as measured by P4 screener). To allow the study to isolate the effects of the intervention and ensure patient treatment preferences are honored, patients will be excluded if they 3) have received psychotherapy or change in psychiatric medication outside of VHA primary in the last 2 months, or 4) voice a preference to be directly referred to specialty mental health care. Veterans with depression, anxiety disorders, mild TBI, and alcohol/ substance use disorders will not be excluded, because these problems commonly co-occur with PTSD, and individuals with these conditions have previously benefited from mindfulness training. Patients who receive PC-MHI services will not be excluded, as this is part of the usual primary care services that all Veterans can receive.

**C.2.2. Phase 2 Recruitment:** Recruitment will use a method used by the PI in several other studies, including the ones detailed in B.3. and B.4. Veterans who screen positive on the annual PC-PTSD screen or have active PTSD symptoms will be referred by their primary care or PC-MHI providers. Referrals will be facilitated with a case-finding procedure: study staff will use medical record data to identify patients that may be eligible for the study based on the annual PTSD screening given to all VHA primary care patients (PC-PTSD). For patients who screen positive, we will ask their primary care providers if a recruitment letter can be sent. All referred Veterans will be sent a letter introducing the study and then will be screened over the phone. In our pilot study, PC-MHI providers were a major source of study referrals. Referral from VHA peer support specialists will also be encouraged. Based on our prior recruitment experience (see B.4., B.5.) we are confident we can recruit 5 participants per month to reach 60 enrolled in one year.

**C.2.3 Phase 2 Procedures:** The baseline session will include informed consent process (Appendix 2) followed by administration of study measures. Participants will be screened for cognitive impairment with the Blessed Orientation Memory and Concentration measure and suicidality with P4 Screener. The P4 Screener assessed past history, plan, probability, and preventive factors and then classifies respondents as minimal, lower or higher risk for suicide. At the baseline assessment, higher risk participants will be connected to VHA Suicide Prevention Services prior to continuing them in the study. In addition to assessing primary outcomes and patient safety, we plan to test the feasibility of measuring concerns that commonly co-occur with PTSD (depression, insomnia, pain, and alcohol/substance misuse) and potential mediators of the relationship between receiving mindfulness training and changes in PTSD symptoms and psychosocial functioning (mindfulness and emotion regulation skills). Pilot data in this area will help us plan for a future full-scale investigation of potential mediators. Post-treatment assessment will occur upon completion of the assigned intervention. We will re-assess participants at two follow-up points: 16 weeks and 24 weeks post-baseline. This will allow the opportunity to test the feasibility of retaining participants over time so that in the full-scale future trial we can test if any changes observed post-treatment are maintained over time. Given that an aim of this line of research is for PCBMT to serve as a bridge to other more intensive PTSD treatments, within the full-scaled trial, data from the 24 week follow-up will also allow the ability to measure changes associated with any new treatments initiated post study treatment. All research assessments will be administered by research staff blinded to randomization outcome. Participants will be reimbursed \$25 per assessment (\$100 total). Randomization will be stratified based on baseline PCL-5 scores (31-40 vs.  $>40$ ) to equate groups at baseline.

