### C.3 Analysis Plan

Aim 1: Gather VHA mental health treatment provider and peer feedback to adapt PCBMT. Co-I [name] will oversee Aim 1 analyses using a Rapid Assessment Process (RAP). This approach is ideal when data needs to be collected and analyzed in one year or less, when only key informants will be interviewed, and when analyses will be deductive. The PI and project coordinator will conduct interviews together with the PI primarily asking questions and the coordinator typing detailed field notes to document responses. A template will be created with a domain name for each interview question (e.g., activating patients, peer roles). The PI, coordinator, and [name] will review the first few sets of field notes collaboratively and summarize content into the domains on the template. After consistency is reached, coders will review the remaining field notes ( $\approx 7$ ) independently. Led by [name], coders will then meet again to analyze summaries and identify suggestions for revisions or aspects seen as helpful that should be maintained within each domain. The PI and Co-Is [name], [name] and [name] will then meet and collectively decide how to modify the protocol. Modifications will only be made if the resulting PCBMT protocol is: 1) feasible to deliver in VHA primary care and 2) stays true to the core mindfulness components. Modifications will be prioritized that are expected to 3) help Veterans develop skills for PTSD symptom management, 4) increase the training’s patient-centeredness, and 5) will affect multiple qualitative domains.

Aim 2: Conduct a pilot RCT (N=60 randomized, n=48 completers) comparing PCBMT to EDU.

**2a.** As this trial will provide us with feasibility information for a larger trial, we will describe the number of participants screened and enrolled per month, proportion of screened participants who are eligible to enroll, completion rates of follow-up assessments, retention rates in study conditions, and the rate and timing of patient drop-out. Recruitment over twelve months will be displayed by plotting the cumulative number of patients enrolled into our study and compared to the anticipated rate of recruitment. Graphs will also be utilized to display rates of intervention and assessment retention at each measurement time. Ninety five percent confidence intervals will be calculated and used in design considerations of a larger trial.

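### The recruitment target of 5 per month for 60 in one year does not match a calendar that recruits in two months of each quarter

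*Combined protocol and SAP*

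**What the plan says.** Section C.2.1 sets the target: "For the RCT, 60 eligible patients will be enrolled and randomized to PCBMT or EDU". It gives one reason for that number: "This sample size was chosen because it will require us to recruit 5 participants per month". It adds that this is the rate thought necessary for a later fully powered trial with a medium effect and three years of recruitment, and that earlier studies achieved it. Section C.2.2 repeats the rate with a time limit: "we are confident we can recruit 5 participants per month to reach 60 enrolled in one year".

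Section C.2.1 then describes the calendar: "Each quarter, two months will be spent recruiting and 1 month will be used to conduct the intervention groups". It expects up to three consecutive rounds of groups per site, with room for more.

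Enrolment per month is a named feasibility metric under Aim 2.a in Section C.2.4. Section C.3 (2a) plots cumulative enrolment over twelve months, to be "compared to the anticipated rate of recruitment".

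**The concern.** Five per month gives 60 in a year only if every calendar month contributes 5 on average. The stated calendar sets aside one month in three for running groups. The text available does not say that 5 is an average over all months, that enrolment continues while groups run, or that a higher rate is expected in the recruiting months.

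In a feasibility trial this is more than a matter of wording. The rate is the stated basis for the sample size, it is the yardstick in 2a, and it is to be carried into the design of a larger trial. With its denominator undefined, the same enrolment record can be read as meeting the target or as missing it.

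**Working it through.** **Inputs**
- Target: 60 enrolled and randomised (C.2.1).
- Rate: 5 per month (C.2.1, C.2.2).
- Window: one year (C.2.2), twelve months in the plot (C.3, 2a).
- Calendar: 2 recruiting months in each 3-month quarter (C.2.1).
- Rounds of groups: up to three per site, more if needed (C.2.1).

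**The plan's own figure.** Enrolment = rate x months: 5 x 12 = 60. It is reproduced if all twelve months count.

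**With the stated calendar.** Recruiting months in a year = 4 quarters x 2 = 8.

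1. *Five is the rate while recruiting.* 5 x 8 = 40, which is 20 short (20/60 = 33%). Time to reach 60: 60/5 = 12 recruiting months; 12/2 = 6 quarters = 18 calendar months.
2. *Five is a calendar average.* 60 in a year stands. The rate needed while recruiting is 60/8 = 7.5 per month.
3. *Only three quarterly cycles are run.* Recruiting months = 3 x 2 = 6. The rate needed is 60/6 = 10 per month; at 5 the yield is 30.

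Group places are not the constraint: three rounds x 2 sites x 2 conditions x the ideal size of 6 = 72 places.

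**Effect on the 2a comparison.** Suppose each quarter's two recruiting months come first.

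| End of month | Straight line at 5 | On plan at 7.5, 7.5, 0 | Short of plan at 6, 6, 0 |
|---|---|---|---|
| 1 | 5 | 7.5 | 6 |
| 2 | 10 | 15 | 12 |
| 3 | 15 | 15 | 12 |
| 12 | 60 | 60 | 48 |

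A trial enrolling 6 per recruiting month exceeds 5 in every recruiting month, yet ends at 8 x 6 = 48. At month 2 it lies above a straight line (12 against 10) but below the stepped curve it needs to follow (12 against 15).

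**Larger trial, illustration only.** Assume d = 0.5, two-sided 5%, 80% completion (48/60, from C.3) and equal arms.
- Five per calendar month for 36 months: 180 randomised, 180 x 0.8 = 144 completers, 72 per arm, power about 85%.
- Five per recruiting month on the same two-in-three calendar: 24 x 5 = 120 randomised, 120 x 0.8 = 96 completers, 48 per arm, power about 68%.

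**The case against.** The strongest reply is that no stated figure is wrong. The one-year total, the twelve-month plot and the three-year horizon are all in calendar time, so 5 reads naturally as a calendar average. The illustration supports this, since 5 x 36 = 180 gives a sensible power for a full trial. This stands as far as it goes: a reader might infer that the plan will simply fall a third short, and the documents do not support that as a flat statement. But the calendar reading still needs 7.5 per recruiting month under C.2.1, and the plan does not say so.

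A second reply is that C.2.1 does not expressly stop enrolment in group months. Facilitators run the groups while research staff find and assess patients. That is possible, but it is not the plain sense of the sentence. It also has a consequence for timing. A patient enrolled at the start of a group month, too late for that round, waits about 13 weeks for the next. The fourth weekly session, three weeks after the first, then falls near week 16, when the follow-up counted from baseline is due (C.2.3).

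The allowance for additional groups changes neither the rate nor the one-year window.

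The remaining replies are correct and limit the point:
- A reader might infer that 7.5 is 50% above what was achieved before. The basis of the earlier rate lies in Section B, which is not in the text available, so this cannot be judged. Figure 2 is not shown and might also clarify the calendar.
- A reader might infer that the larger trial will be underpowered. The documents fix neither its calendar nor a numerical effect size.
- A reader might infer that recruitment is the only feasibility measure with a number attached. C.3 also gives 48 completers.
- The pilot is descriptive, with no progression rule tied to 5 per month, and a shortfall at month 12 would show in the plot.

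**Conclusion.** The recruitment figure and the recruiting calendar do not match as written, and nothing in the text available reconciles them. The gap is between 40 and 60 patients in a year, or equivalently between 5 and 7.5 per recruiting month. At 5 per recruiting month the window is 18 months instead of 12. These figures assume four cycles a year and no enrolment in group months; with three cycles the required rate is 10.

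The defect is an undefined basis for the rate, not a multiplication error. It does not show that the pilot will miss 60, that the required rate exceeds past experience, or that the later trial would lack power. It should still be corrected, because this rate carries the sample-size rationale and the 2a comparison.

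**What to change.** Reconcile C.2.1 and C.2.2 by stating one basis for the rate:
- a calendar average of 5, equal to 7.5 per recruiting month over 8 recruiting months; or
- if so intended, that enrolment continues in group months, with its effect on waiting time and the 16-week assessment checked; or
- if so intended, that the window is 18 months.

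State the number of quarterly cycles that the chosen figure assumes. In C.3 (2a), draw the anticipated cumulative curve on the same basis, flat in group months if recruiting pauses, and extend the plot if the window is lengthened. Report enrolment both per recruiting month and per calendar month. Derive the larger trial's required rate on the same basis, and say which basis the earlier studies' rate used.

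The cost is a few sentences and one figure specification, with no new data collection. If 7.5 is adopted, the stated rate looks more demanding. The 18-month option would also lengthen the study.

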- *PTSD Checklist-5 (PCL-5)* is a 20-item self-report measure that asks respondents to rate how much they have been bothered by DSM-5 PTSD symptoms in the past month. We will administer this with the extended assessment of traumatic events to ensure that the symptoms reported are related to an event that meets criteria for a traumatic event. Early psychometric study of the PCL-5 indicates excellent reliability and validity. A cut point of 31 along plus meeting Criterion A will be required for study inclusion to allow Veterans with subthreshold PTSD to participate. The total score will be used to indicate PTSD severity at each time point. Since participants must wait to begin the intervention until enough participants are enrolled to form a group, the PCL-5 will be re-administered if participants do not attend class 1 within one month of their baseline interview.
- *Recovery Assessment Scale (RAS)* is a 24-item self-report measure that will assesses various aspects of recovery from the perspective of the Veteran, with an emphasis on hope and self-determination. It covers 5 domains: personal confidence and hope; willingness to ask for help; goal and success orientation; reliance on others; and no domination by symptoms. It has high reliability and good concurrent validity.
- *Patient Health Questionnaire-9 (PHQ-9)* assesses 9 symptoms of depression on a 4-point scale. Participants who endorse the suicidality item will also be administered the P4 screener which assess past history, plan, probability, and preventive factors for suicide.
- *Health Promoting Lifestyle Profile II*

Hypothesized mediators will be assessed with 2 psychometrically sound measures at each time point.

- *Self-Compassion Scale- Short Form*
- *Five Facet Mindfulness Questionnaire (FFMQ)* is a 39-item scale measuring observing, describing, acting with awareness, non-judging, and non-reactivity.
- *Emotion Regulation Questionnaire (ERQ)* is a 10-item self-report measure designed to assess the use cognitive reappraisal and expressive suppression.

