**C.2.5. Intervention Conditions:** The PCBMT and EDU groups will share several structural features: both will be 1) located in primary, 2) co-led by a licensed mental provider (psychologist, clinical social worker, mental health counselor) and a Veteran peer support specialist, 3) consist of four 90-minute weekly sessions, 4) Peers will meet briefly (30 minutes) to guide participants in completing the Personal Health Inventory (PHI) prior to starting their assigned treatment condition. The PHI was developed by the VHA Office of Patient Centered Care and Cultural Transformation and is a commonly used by VHA peers support specialists. The PHI will allow participants to engage in self-reflection regarding what matters most to them in their lives (Appendix 4). This discovery process will inform the identification of personal health goals that align with their values and priorities, and thus ideally increase patient activation and engagement. This process supports the delivery of personalized, proactive, and patient-driven care. Completed PHIs will be shared with the group facilitators to help personalize the intervention. 4) During the meeting with the peers, participants will also watch a video to orient them to their assigned condition. PCBMT participants will watch the 7-minute "What is Mindfulness?" video from the VHA OPCC. EDU participants will watch two 3.5-minute whiteboard videos "What is PTSD?" and "Treatment: Know Your Options" from the VHA National Center for PTSD. 6) Printed instructions for homework will be provided and participants will be asked to submit simple forms during each class that record the type and number of minutes of at home practice completed. For PCBMT this will include time spent in

formal and informal meditation. 7) Peer co-leaders will act as peer-navigators to help participants connect to any additional MH, case management, or medical care needed.

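### Do 5 enrolments a month, quarterly rounds and an ideal group size of 6 conflict in a way that requires a change to the plan?

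*Combined protocol and SAP*

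**What the plan says.** All references are to the combined protocol and SAP.

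- **Group size and number of rounds (C.2.1):** "Ideal group size is 6 participants. We anticipate running up three consecutive groups (PCBMT and EDU) at each of the two sites". The next sentence adds: "However, our timeline allows for addition groups as needed".
- **Cycle (C.2.1):** "Each quarter, two months will be spent recruiting and 1 month will be used to conduct the intervention groups".
- **Rate (C.2.2):** "we are confident we can recruit 5 participants per month to reach 60 enrolled in one year".
- **Waiting (C.2.4, PCL-5 entry):** "Since participants must wait to begin the intervention until enough participants are enrolled to form a group", the PCL-5 is repeated for anyone who has not attended class 1 within a month of baseline. No minimum group size and no maximum wait are given.
- **Follow-up clock (C.2.3):** "We will re-assess participants at two follow-up points: 16 weeks and 24 weeks post-baseline". The post-treatment assessment is tied to the end of the course instead.
- **Course (C.2.5):** both arms "consist of four 90-minute weekly sessions".
- **Analysis (C.3, Aim 2a):** cumulative enrolment over twelve months is plotted against the expected rate. Feasibility results are descriptive, with 95% confidence intervals.

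**The concern.** The paragraph gives a group size, a number of rounds and a cycle length, and the next section gives a rate. Multiplied out, the four do not meet. At the stated rate, a quarter does not supply enough patients for four groups of six, and three quarters do not supply 60.

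Two consequences would matter if the conflict were real. Retention, fidelity and acceptability (Aims 2b and 2c) might be estimated in groups much smaller than those intended, then carried into the design of the full-scale trial. Alternatively, groups might be held back until full. The earliest enrolled could then reach the 16-week assessment before their first class, and the between-arm effect size at that visit would mix treated and untreated patients.

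**Working it through.** **Inputs.** Rate 5 per month, 60 in 12 months (C.2.2). One round per quarter, ideal size 6, up to three rounds, two sites, two arms (C.2.1). Four weekly sessions (C.2.5). Follow-up at 16 weeks from baseline (C.2.3). Assumptions: both arms run at both sites every quarter, patients divide equally, accrual is even, and a month is 52/12 weeks.

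**1. The plan's own figure.** 5 x 12 = 60, which reproduces. The rate must therefore be a calendar average. If it applied only to the two recruiting months of each quarter, a year would give 5 x 8 = 40. If recruiting stops in group months, 60 needs 60/8 = 7.5 per recruiting month, which is still 15 per quarter.

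**2. Group size by quarter.** 5 x 3 = 15 patients; 2 arms x 2 sites = 4 groups; 15/4 = 3.75 per group. Against 6: 1 - 3.75/6 = 37.5% lower.

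**3. Rounds.**
- Three rounds: 3 x 15 = 45 patients in 12 groups.
- Four rounds: 4 x 15 = 60 patients in 16 groups; 60/16 = 3.75.
- By capacity alone, 12 groups of 6 hold 72 and 60/12 = 5, so three rounds look sufficient until the rate is brought in. Sixty patients in three quarterly rounds would need 60/9 = 6.7 per month.

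**4. Waiting on the written quarterly cycle.**
- Recruiting in two months only: longest wait 2 x 52/12 = 8.7 weeks. Class 4 is three weeks after class 1, at week 11.7.
- Enrolment continuing in group months: longest wait 3 x 52/12 = 13.0 weeks, with class 4 at week 16.0.
- Counting the course as four full weeks, it ends at week 17.0 at the latest in the second case. The share affected is (13 - 12)/13 = 8%.
- In no case does class 1 fall after week 16.

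**5. Waiting if groups were held until full.**
- Groups of 6: 24/5 = 4.8 months = 20.8 weeks. Week 16 precedes class 1 for (20.8 - 16)/20.8 = 23% and class 4 for (23.8 - 16)/20.8 = 38%. The mean wait is 20.8/2 = 10.4 weeks.
- Groups of 5: 20/5 = 4.0 months = 17.3 weeks. Week 16 precedes class 1 for (17.3 - 16)/17.3 = 8%.
- Both fill times exceed a quarter, so both depart from the cycle in C.2.1.

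**6. Sensitivity to the inferred four groups.** If the sites took turns and the active site supplied the whole quarter's 15, each group would have 15/2 = 7.5, above the ideal. The shortfall in step 2 depends on a scheduling detail that the text does not give.

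**The case for a change.** The strongest opposing case is that a fourth round restores the total but not the group size: 16 groups still average 3.75. At the plan's own 48 completers of 60, that becomes 3.75 x 0.8 = 3.0 per group. At the 55% first-class attendance reported from the earlier pilot it becomes 3.75 x 0.55 = 2.1. Chance adds to this, because "Randomization will be stratified based on baseline PCL-5 scores" and the text does not mention stratifying by site. The text never says how many patients are enough to start a group, and the listed feasibility measures include neither group size nor the interval from baseline to class 1. A fourth round also raises the sessions to be staffed from 12 x 4 = 48 to 16 x 4 = 64.

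Part of this stands. Groups below 6 are the likely outcome, and a report that gave group sizes and waits would be more useful. The rest is weaker. The 55% comes from a version without peer support, which was added partly to raise attendance, and it says nothing about the education arm. Completers are not defined as class attenders. Small groups and long waits are alternatives, not joint harms, and the long wait arises only if staff abandon the quarterly cycle. The plan foresees delay: the one-month rule for repeating the PCL-5 obliges staff to track the interval, so it can be reported without a new rule.

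**Conclusion.** No change is needed. The divisions are correct, but they set an ideal and an expected number of rounds against a fixed cycle and rate, and C.2.1 already says where the slack lies. Following the text gives four quarterly rounds, 60 patients in 12 months, and groups averaging about 3.75. No patient reaches week 16 before class 1, and at most about 8% reach it before the end of a four-week course.

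The planned outputs are descriptive rates, means and effect sizes with confidence intervals. None uses a group size of 6 as an input, and none becomes wrong when groups are smaller. The planned plot of enrolment against the expected rate will show any shortfall. An accrual table or extra descriptive variables would put on paper what the team will see as it schedules groups, without correcting a figure or rule that would mislead.

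This rests on reading 5 per month as a calendar average, even accrual, both arms at both sites each quarter, and groups starting on the quarterly cycle. Figure 2, section B and the appendices were not available and may settle the scheduling. If groups were in practice held past the quarter to fill, the week-16 comparison would need care (23% untreated at that visit for groups of 6, 8% for groups of 5), but the plan does not call for that.
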